9.3.2. Safety Analyses

All safety analyses will be performed on the safety population.

AEs, ECGs, BP, pulse rate, continuous cardiac monitoring, and safety laboratory data will be reviewed and summarized on an ongoing basis during the study to evaluate the safety of participants. Any clinical laboratory, ECG, BP, and pulse rate abnormalities of potential clinical concern will be described. Safety data will be presented in tabular and/or graphical format and summarized descriptively, where appropriate.

Medical history and physical examination and neurological examination information, as applicable, collected during the course of the study will be considered source data and will not be required to be reported, unless otherwise noted. However, any untoward findings identified on physical and/or neurological examinations conducted during the active collection period will be captured as AEs, if those findings meet the definition of an AE. Data collected at screening that are used for inclusion/exclusion criteria, such as laboratory data, ECGs, and vital signs, will be considered source data, and will not be required to be reported, unless otherwise noted. Demographic data collected at screening will be reported.

9.3.2.1. Electrocardiogram Analyses

Changes from baseline for the ECG parameters QT interval, heart rate, QTc interval, PR interval, and QRS complex will be summarized by treatment and time.

The number (%) of participants with maximum postdose QTc values and maximum increases from baseline in the following categories will be tabulated by treatment (Table 3):

Table 3. Safety QTc Assessment

Degree of Prolongation	Mild (msec)	Moderate (msec)	Severe (msec)
Absolute value	>450-480	>480-500	>500
Increase from baseline		30-60	>60

In addition, an attempt will be made to explore and characterize the relationship between plasma concentration and QT interval length using a PK/PD modeling approach. If a PK/PD relationship is found, the impact of participant factors (covariates) on the relationship will be examined.

CCI

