1.2. Schema

1.3. Schedule of Activities

The SoA table provides an overview of the protocol visits and procedures. Refer to the **STUDY ASSESSMENTS AND PROCEDURES** section of the protocol for detailed information on each procedure and assessment required for compliance with the protocol.

The investigator may schedule visits (unplanned visits) in addition to those listed in the SoA table, in order to conduct evaluations or assessments required to protect the well-being of the participant.

	Screening	Period 1				Period 2 ^m						Early Termination/Discontinuation	Follow-up ⁿ
Visit Identifier ^a Abbreviations used in this table may be found in Appendix 8	Day -28 to Day -2	Day -1	Day 1	Day 2	Day 3	Day 1	Day 2 to Day 8	Day 9	Day 10	Day 11	Day 12		28-35 days after last dose
Informed consent	X												
CRU confinement		X	→	→	→	→	→	→	→	→	X		
Inclusion/exclusion criteria	X	X											
Medical, drug, tobacco and alcohol history	X	X											
Contraception check	X	X										X	X
Pregnancy test (for WOCBP)	X	X										X	
Demography	X												
Physical examination ^b	X	X											
Safety laboratory	X	X						X		X	X		
TB Screen ^c	X												
Serum FSH (postmenopausal women only)	X												
Serology: Viral screen, HBsAg, HCVAb, HIV, HBsAb and HBcAb	X												
CCI			█										
Urine drug screen	X	X											
12-Lead ECG (single)	X		X							X	X		
Vital signs (supine BP, pulse rate) ^e	X		X			X			X		X	X	
COVID-19 questionnaire ^f	X	X											
COVID-19 testing ^g	X	X											
COVID-19 check temperature ^h	X	X	→	→	→	→	→	→	→	→	X	X	

PFIZER CONFIDENTIAL

	Screening	Period 1				Period 2 ^m						Early Termination/Discontinuation	Follow-up ⁿ
Visit Identifier ^a Abbreviations used in this table may be found in Appendix 8	Day -28 to Day -2	Day -1	Day 1	Day 2	Day 3	Day 1	Day 2 to Day 8	Day 9	Day 10	Day 11	Day 12		28-35 days after last dose
OC dosing ⁱ			X						X				
PF-06650833 QD dosing ^j						X	X	X	X	X			
OC PK blood sample ^{k,l}			X	X	X				X	X	X	X	
Serious and non-serious AE monitoring	X	→	→	→	→	→	→	→	→	→	→	X	X
Prior/concomitant treatment assessment	X	→	→	→	→	→	→	→	→	→	→	X	X
CRU discharge												X	

- a. **Visit Identifier:** Day relative to start of study treatment (Day 1).
- b. **Physical Examination:** Complete physical exam could be done at screening or admission on Day -1. Brief physical exam to be done only in case of finding at previous exam or new/open AE if applicable, at the discretion of the investigator.
- c. **TB Screen:** QFT-G test.

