- d. **COVID-19 screening:** COVID-19 screening will be done at screening and Day -1. A subsequent COVID-19 test can be performed if participants admitted for residence develop COVID-19 like symptom(s).
- e. **Vital signs (supine BP, pulse rate):** Vital signs will be collected before dosing.
- f. **COVID-19 questionnaire:** Check exposure to positive participant, residence or travel in area of high incidence and COVID-19 related signs and symptoms.
- g. **COVID-19 testing:** The testing for COVID-19 pathogen by PCR will be performed screening and D-1. A subsequent COVID-19 test can be performed if participants admitted for residence develop COVID-19 like symptom(s).
- h. **COVID-19 check temperature:** To be done twice daily during residence.
- i. **OC dosing:** Participants will be dosed with OC following an overnight fast of at least 10 hours. On the day of co-administration of OC and PF-06650833, the two will be administered simultaneously within 5 minutes.
- j. **PF-06650833 QD dosing:** The daily dose of PF-06650833 will be administered at approximately 08:00 ±2 hours.
- k. **OC PK blood sample:** PK blood samples are to be collected at predose, at 30 minutes and 1, 1.5, 2, 4, 6, 8, 12, 24, 36 and 48 hours post OC dose in Periods 1 and 2.
- l. **OC PK blood sample:** The 24 hour OC PK samples on Period 2 Day 11 must be collected pre PF-06650833 dose.
- m. **Period 2:** There is no washout phase between Period 1 and Period 2.
- n. **Follow-up:** Participants will have a telephone contact at least 28 calendar days, and up to 35 calendar days after the last administration of the investigational product(s). At the discretion of the investigator, telephone contact may be substituted with an on-site visit in case of additional follow-up of open AEs or clinically significant laboratory findings

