2.3. Benefit/Risk Assessment

PF-06650833 is not expected to provide any clinical benefit to healthy participants. This study is designed primarily to generate safety, tolerability, and pharmacokinetic data for further clinical development.

[figure not shown]
In the clinical studies of PF-06650833 (see [Section 2.2.4](#)), the investigational product was determined to be well tolerated and to have an acceptable safety profile.

CCI

More detailed information about the known and expected benefits and risks and reasonably expected AEs of PF-06650833 may be found in the IB, which is the SRSD for this study.

The expected exposures of PF-06650833 in this study are lower than the highest exposures observed in the Phase 1 studies (see Justification for Dose in [Section 4.3](#)). CCI

herefore, the risk to the participants in this study is expected to be minimal. In addition, any risks are minimized by appropriate safety measures including safety laboratory measurements, ECGs, vital signs for study participants.

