4.2. Scientific Rationale for Study Design

Given the potential teratogenicity risk of PF-06650833 and potential of CYP3A induction risk, only WONCBP will be allowed in this study.

A fixed sequence design was selected for this study over a randomized 2-sequence crossover design based on operational considerations. It should be noted that the fixed sequence study design does not control for a period effect, however, the period effect is generally considered to be a low risk for PK DDI studies.

Based on the in vitro metabolic profiling, there is low potential of oral contraceptive steroids to impact PK of PF-06650833, only the effect of PF-06650833 will be evaluated in this study. In order to allow the full effect of potential enzyme induction of CYP3A4 to manifest, PF-06650833 will be dosed for 10 days prior to OC dosing. This is supported by Simcyp simulations showing maximal induction of CYP3A4 by PF-06650833 under the study design.

Due to the effect of food on PK of PF-06650833 MR and consistent with Phase 2 studies, PF-06650833 will be dosed in fasted state in this study.

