6.7. Treatment of Overdose

For this study, any dose of PF-06650833 greater than 6 g within a 24-hour time period will be considered an overdose.

There is no specific treatment for an overdose with PF-06650833.

In the event of an overdose, the investigator should:

1. Contact the medical monitor within 24 hours.
2. Closely monitor the participant for any AEs/SAEs and laboratory abnormalities for at least 5 half-lives or 28 calendar days after the overdose of study investigational products (whichever is longer).
3. Document the quantity of the excess dose as well as the duration of the overdose in the CRF.
4. Overdose is reportable to Pfizer Safety **only when associated with an SAE**.
5. Obtain a blood sample for PK analysis within 7 days from the date of the last dose of study intervention(s) if requested by the medical monitor (determined on a case-by-case basis).

Decisions regarding dose interruptions or modifications will be made by the investigator in consultation with the medical monitor based on the clinical evaluation of the participant.

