8.4. Pharmacokinetics

Plasma for analysis of EE and LN

Blood samples of approximately 6 mL ($2 \times 6 = 12$ mL), to provide approximately 2.5 mL plasma for each EE and LN will be collected into appropriately labeled tubes containing K₂EDTA for measurement of plasma concentrations of EE and LN as specified in the SoA. Instructions for the collection and handling of biological samples will be provided in the laboratory manual or by the sponsor. The actual date and time (24-hour clock time) of each sample will be recorded.

The actual times may change, but the number of samples will remain the same. All efforts will be made to obtain the samples at the exact nominal time relative to dosing. Collection of samples up to and including 10 hours after dose administration that are obtained within 10% of the nominal time relative to dosing (eg, within 6 minutes of a 60-minute sample) will not be captured as a protocol deviation, as long as the exact time of the collection is noted on the source document and the CRF. Collection of samples more than 10 hours after dose administration that are obtained ≤ 1 hour away from the nominal time relative to dosing will not be captured as a protocol deviation, as long as the exact time of the collection is noted on the source document and the CRF. This protocol deviation window does not apply to samples to be collected more than 10 hours after dose administration at outpatient/follow-up visits with visit windows.

Samples will be used to evaluate the PK of OC steroids (EE and LN). Samples collected for analyses of OC steroids (EE and LN) concentration may also be used to evaluate safety or efficacy aspects related to concerns arising during or after the study, for metabolite identification and/or evaluation of the bioanalytical method, CCI [REDACTED]

CCI [REDACTED]

Samples collected for measurement of plasma concentrations of OC steroids (EE and LN) will be analyzed using a validated analytical method in compliance with applicable SOPs.

The PK samples must be processed and shipped as indicated in the instructions provided to the investigator site to maintain sample integrity. Any deviations from the PK sample handling procedure (eg, sample collection and processing steps, interim storage or shipping conditions), including any actions taken, must be documented and reported to the sponsor. On a case-by-case basis, the sponsor may make a determination as to whether sample integrity has been compromised.

CCI [REDACTED]

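### Does the study need PF-06650833 concentrations to read its EE and LN ratios, or to support the QT model mentioned in the protocol?

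*Protocol*

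**What the plan says.** **Objective and endpoints.** Protocol Section 3 asks what repeated PF-06650833 dosing does to single-dose oral contraceptive (OC) PK. The primary endpoints are Cmax and AUClast of EE and LN. Parameter derivation (Protocol 9.3.1) and SAP Table 6 cover those two analytes only.

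**Sampling.** The one readable PK row in the Schedule of Activities is for the OC. Blood is drawn "at predose, at 30 minutes and 1, 1.5, 2, 4, 6, 8, 12, 24, 36 and 48 hours post OC dose" in both periods, and footnote l adds: "The 24 hour OC PK samples on Period 2 Day 11 must be collected pre PF-06650833 dose". Protocol 8.4 states: "Samples will be used to evaluate the PK of OC steroids (EE and LN"). It also allows those samples to serve safety or efficacy questions that arise, and that sentence runs into a redaction. The only other visible PK draw follows an overdose, if the medical monitor asks for it: "Obtain a blood sample for PK analysis within 7 days from the date of the last dose" (Protocol 6.7).

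**Basis for PF-06650833 exposure.** Protocol 2.3 says: "The expected exposures of PF-06650833 in this study are lower than the highest exposures observed in the Phase 1 studies". On enzyme induction, Protocol 4.2 says: "This is supported by Simcyp simulations showing maximal induction of CYP3A4 by PF-06650833 under the study design". Dosing is fasted to match Phase 2 (4.2), uses the highest dose planned for later trials (4.3), and is supervised with a mouth check (6.4).

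**QT.** Protocol 9.3.2.1 says "an attempt will be made to explore and characterize the relationship between plasma concentration and QT interval length using a PK/PD modeling approach", with a look at covariates if a relationship appears. SAP 6.2.4 plans summaries of absolute values, maximum increases and categories. Its readable text has no concentration-QT model.

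**The concern.** The study exists to set contraception requirements for Phase 2, so a ratio near 1 is the result most likely to be acted on. Supervised dosing shows that tablets were swallowed, not what exposure followed. Without PF-06650833 concentrations, the report could not separate little effect at the intended exposure from a diluted effect at lower exposure than expected. The protocol itself says that food affects the MR tablet's PK (4.2).

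The QT sentence looks like a second fault. It promises a model whose most natural input, PF-06650833 concentration, is not visibly collected, and the SAP does not take the model up.

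**Working it through.** No alpha, power or variance figure enters this point. The check is which analyte is scheduled, what the primary analysis needs, and what an added assay would cost.

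**1. Analyte by place (readable text)**

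| Place | Analyte |
|---|---|
| Protocol 3, primary and exploratory PK endpoints | EE, LN |
| Schedule of Activities, PK row and footnotes k and l | OC |
| Protocol 8.4 | EE, LN |
| Protocol 9.3.1 | EE, LN |
| SAP 6.1.1 and Table 6 | EE, LN |
| Protocol 6.7 | not named; overdose only, on request |
| Protocol 9.3.2.1 | not named |

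Visible scheduled PF-06650833 draws: 0. One Schedule of Activities row is redacted. Its single mark, as extracted, falls on Period 1 Day 1, before any PF-06650833 dose.

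**2. Blood volume.** There are 12 time points x 2 periods = 24 draws. At 12 mL each (Protocol 8.4) that is 24 x 12 = 288 mL of the stated 350 mL or so, leaving 350 - 288 = 62 mL. Most other sample volumes are not given, so the total neither proves nor excludes a PF-06650833 draw.

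**3. What the primary analysis uses.** The model compares ln(AUClast) or ln(Cmax) between Period 1 Day 1 and Period 2 Day 10 within participants, then exponentiates the difference. PF-06650833 concentration is not an input. The quantity estimated is the effect of the regimen as given.

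**4. How a null result could mislead (assumed values, n = 8 completers).** Suppose the true ratio is 0.70 and m of 8 participants have no effective exposure. The expected geometric mean ratio is then 0.70^(1 - m/8):

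| m | Expected ratio |
|---|---|
| 0 | 0.70 |
| 2 | 0.77 |
| 4 | 0.84 |
| 6 | 0.92 |

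The dilution is possible in principle. Nothing in the documents suggests that 2 or more of 8 confined, fasted, supervised participants would have no effective exposure.

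**5. ECGs available for a QT model.** The Period 1 Day 1 ECG is the pre-dose baseline (SAP 3.4). By column count the later scheduled ECGs fall on Period 2 Days 11 and 12: 2 x 10 = 20, or 2 x 8 = 16 for completers. The columns may be shifted, because the discharge mark sits under Early Termination while Protocol 4.1 puts discharge on Day 12. If the ECG marks belong one column to the right, 10 (or 8) scheduled Period 2 ECGs remain. On either reading no ECG falls on Day 10, so the data are thin for any analyte.

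**6. Cost of adding the assay.** Both drugs are given within 5 minutes on Period 2 Day 10, so the draws from pre-dose to 24 h (10 of 12) span one once-daily interval.
- Full set: 10 draws x 10 participants = 100 assays (80 for 8 completers).
- Reduced set of 6 (pre-dose, 2, 4, 8, 12, 24 h): 60 assays (48).
- If plasma is short, an assumed 2 to 4 mL more at 10 draws adds 20 to 40 mL, giving 370 to 390 mL in total. That is under the 550 mL limit, but the limit is worded for extra safety samples.
- A protocol amendment with IRB/EC approval (Protocol 10.1.1), plus SAP and laboratory manual changes.

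**The case for a change.** The best case for a change is that the assay is cheap and bears on the result most likely to be used. The draws already exist and the 24 h sample already precedes the next PF-06650833 dose. Protocol 2.2.4 reports AUC and Cmax from earlier studies, so a method has been used before. Cmax, AUCtau and trough beside the ratios would let a reader judge a null result against the exposure assumed in the simulation.

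Part of this stands. On the readable text exposure is unmeasured, so the report should claim no more than an effect of the regimen. Carrying the result to a setting with different PF-06650833 exposure would rest on the simulation and earlier data. The two documents also do not match on the QT model.

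The rest does not make the plan unsound. The Phase 2 contraception question concerns this drug at doses up to the one tested and under the same fasting condition, and the ratio for the regimen addresses it directly. Protocol 4.2 also explains the one-way scope: the OC steroids are judged unlikely to affect PF-06650833. With no threshold for adequate exposure, the assay would inform judgement but would not settle which explanation holds. The current status of the method, the plasma left over and the MR tablet's profile are not visible, so whether these draws would describe exposure well is itself an assumption.

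On QT, Protocol Section 9 lets the SAP modify the outlined analyses, with an amendment needed only for major changes to the primary endpoints or their analysis. Protocol 9.4 and SAP 7 both mention PK/PD modelling in general terms. The sentence commits only to an attempt.

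**Conclusion.** No change follows. Leaving PF-06650833 out of the scheduled assays is a fair trade-off for a study whose objective is a regimen effect. None of the four primary ratios depends on it. The addition would cost 60 to 100 assays and an amendment for descriptive context. It would be a helpful extra if a method and enough plasma are at hand, but its absence is not an error.

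The QT sentence is a loose end. An analyst can attempt the exploration with whatever concentrations exist, or report that the data did not support it. Naming the analyte or dropping the sentence would align the documents, and a line in the report saying whether PF-06650833 exposure was measured would help readers. Both are optional and leave every planned estimate as it is.

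This rests on the readable text. Redactions follow the passage on sample use in Protocol 8.4, the QT sentence in 9.3.2.1 and the ECG endpoints in SAP 3.5.4, so a PF-06650833 assay or a QT analysis may be provided for there. If so, the concern falls away altogether. The conclusion also assumes that dosing is carried out as described, supervised and fasted throughout Period 2.

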9.4. Interim Analyses

No formal interim analysis will be conducted for this study. As this is an open-label study, the sponsor may conduct unblinded reviews of the data during the course of the study for the purpose of safety assessment, facilitating PK/PD modeling, and/or supporting clinical development.

9.5. Sample Size Determination

[figure not shown]
[figure not shown]
[figure not shown]
Approximately 10 participants will be enrolled and dosed to achieve at least 8 participants completing the study. **CCI**

Table 4

and [Table 5](#) presents the reference boundaries and width of the confidence intervals for a range of different estimated effects (estimates of the ratio for pairs of treatments: Test vs Reference).

CCI

10. SUPPORTING DOCUMENTATION AND OPERATIONAL CONSIDERATIONS

10.1. Appendix 1: Regulatory, Ethical, and Study Oversight Considerations

10.1.1. Regulatory and Ethical Considerations

This study will be conducted in accordance with the protocol and with the following:

- Consensus ethical principles derived from international guidelines, including the Declaration of Helsinki and CIOMS International Ethical Guidelines;
- Applicable ICH GCP guidelines;
- Applicable laws and regulations, including applicable privacy laws.

The protocol, protocol amendments, ICD, SRSD(s), and other relevant documents (eg, advertisements) must be reviewed and approved by the sponsor, submitted to an IRB/EC by the investigator, and reviewed and approved by the IRB/EC before the study is initiated.

Any amendments to the protocol will require IRB/EC approval before implementation of changes made to the study design, except for changes necessary to eliminate an immediate hazard to study participants.

Protocols and any substantial amendments to the protocol will require health authority approval prior to initiation except for changes necessary to eliminate an immediate hazard to study participants.

The investigator will be responsible for the following:

- Providing written summaries of the status of the study to the IRB/EC annually or more frequently in accordance with the requirements, policies, and procedures established by the IRB/EC;
- Notifying the IRB/EC of SAEs or other significant safety findings as required by IRB/EC procedures;
- Providing oversight of the conduct of the study at the site and adherence to requirements of 21 CFR, ICH GCP guidelines, the IRB/EC, European regulation 536/2014 for clinical studies (if applicable), European Medical Device Regulation 2017/745 for clinical device research (if applicable), and all other applicable local regulations.

10.1.1.1. Reporting of Safety Issues and Serious Breaches of the Protocol or ICH GCP

In the event of any prohibition or restriction imposed (eg, clinical hold) by an applicable regulatory authority in any area of the world, or if the investigator is aware of any new information that might influence the evaluation of the benefits and risks of the study intervention, Pfizer should be informed immediately.

In addition, the investigator will inform Pfizer immediately of any urgent safety measures taken by the investigator to protect the study participants against any immediate hazard, and of any serious breaches of this protocol or of the ICH GCP guidelines that the investigator becomes aware of.

10.1.2. Financial Disclosure

Not applicable.

